5 STUDY ENTRY, ENROLLMENT AND WITHDRAWAL

5.1 Study Entry

Study entry, as used in this protocol, will be defined as a subject signing informed consent. Study enrollment, as used in this protocol, will be defined as the investigator's confirmation of the subject's eligibility by signing an eligibility checklist. As per University of Miami policy, each study participant, including participants who have screened failed, who sign an informed consent form, should be entered into the study database.

5.2 Enrollment Procedure

Completed and signed protocol-specific eligibility checklist;

All pages of the original signed informed consent forms (ICFs), including HIPAA Form B; Relevant source documents or medical records such as: subject medical history and physical exam, admission or discharge notes, diagnostic reports, pathologic confirmation of diagnosis, and relevant subject-specific written communication.

Documentation from the Investigator that he/she has determined the subject meets eligibility criteria.

5.3 Cancellation Guidelines

The following are reasons for withdrawal of subjects from the study:

- A subject does not meet the eligibility criteria; (the subject will be considered a screen failure).
- A subject withdraws consent,
- A subject dies during protocol participation from causes other than the study treatment (not due to adverse events) or
- A study investigator decides the subject should be withdrawn from the study (e.g. subject non-compliance)

Regardless of reason for withdrawal, an intention to treat analysis will be performed.

All subjects who either screen fails, is withdrawn from the study or has completed all visits should be de-enrolled from the research database within 48 hours.

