2. HYPOTHESIS

2.1 Alternate hypothesis

Natesto™ will not change sperm count by $\pm 10\%$ from baseline.

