10.4 Statistical Analysis and Power calculation

The average and standard deviation of all relevant variables and baseline characteristics, primary and secondary outcomes will be calculated.

Change in sperm count will be analyzed using the ANOVA and MANOVA. A change in $< \pm 10\%$ will be reject the null hypothesis.

LH, FSH, E and Testosterone levels will be analyzed using one-sample t-test with repeated measures throughout the study.

IIEF-EF and SF-36 questionnaires will be analyzed and compared between the groups according to Fisher's exact test in each of the endpoints. The statistical significance will be set at $P < 0.05$.

Demographic characteristics such as age and testosterone level will be compared between groups A and B using student's test. Other demographic characteristics, such as medical background and risk factors will be compared between these groups using Fisher's exact test.

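### Intention to treat is the only analysis named for a no-change claim on sperm count, so men who skip the drug but are still sampled pull a real fall into the ±10% band

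*Combined protocol and SAP*

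**What the plan says.** Section 2.1 puts the claim to be shown in the alternate hypothesis: Natesto "will not change sperm count by" ±10% from baseline. Section 2.2 makes a change of that size the null. Section 10.4 gives the decision rule, "A change in $< \pm 10\%$ will be reject the null hypothesis", and the method, "Change in sperm count will be analyzed using the ANOVA and MANOVA".

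The analysis population appears once, at the end of the withdrawal list in section 5.3: "Regardless of reason for withdrawal, an intention to treat analysis will be performed". That list includes "A study investigator decides the subject should be withdrawn from the study (e.g. subject non-compliance". The same section has withdrawn men de-enrolled from the database within 48 hours. Section 10 defines no per-protocol, on-treatment or completer set, and no rule for missing semen values. No adherence measure or expected adherence rate is given anywhere.

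**The concern.** In a trial that aims to show a difference, counting men who did not take the drug works against the hypothesis, and this is why intention to treat is regarded as cautious. Here the aim is reversed. A man who is off drug and whose count stays near baseline contributes a change near zero, which is the result the trial hopes to find. If the drug does lower sperm count (section 8.1 says that large doses may), non-use hides part of the fall.

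At stake is a conclusion that sperm count is preserved on treatment when part of the sample was not on treatment. Some non-use is foreseeable: the course lasts 24 weeks (section 4.2), the rationale in section 1.3 refers to three-times-daily use (3 × 7 × 24 = 504 administrations), and the calendar shows drug dispensed at only two visits.

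**Working it through.** **Inputs from the documents.** Margin ±10% (sections 2.1, 2.2, 10.4). Sample size 80 (sections 6.3, 10.3) or 40 (section 4.1); the two conflict, so both are used. There is no stated figure for adherence, dropout, on-drug effect or the standard deviation (SD) of change, so the plan has no figure of its own to reproduce on this point.

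**Assumptions.** A share f of men is off drug, stays in the study, is sampled, and has a mean change of zero. Men on drug have mean change e. The section 10.4 rule is read as applying to the observed mean change.

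**Step 1: dilution.** The mean over all men is (1 − f) × e. The on-drug fall that reads as exactly −10% is 10/(1 − f) on the arithmetic scale, or 1 − 0.9^(1/(1 − f)) if change is averaged as a ratio.

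| Off drug | Arithmetic | Ratio |
|---|---|---|
| 20% | 10/0.8 = 12.5% | 1 − 0.9^(1/0.8) = 12.3% |
| 30% | 10/0.7 = 14.3% | 1 − 0.9^(1/0.7) = 14.0% |

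These are boundary values: the diluted mean sits on the margin, and smaller on-drug falls lie inside it. Conversely, an on-drug fall of |e| is diluted into the band once f exceeds 1 − 10/|e|. That is 16.7% of men for a 12% fall, 33.3% for 15% and 50% for 20%.

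**Step 2: chance of a wrong no-change verdict.** Take a true on-drug fall of 15%, with the SD of individual change assumed. Simulation of the mean-change rule (20,000 runs per cell) gives:

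| N | SD (points) | 0% off | 10% off | 20% off | 30% off |
|---|---|---|---|---|---|
| 80 | 20 | 1.2% | 6.1% | 18.8% | 41.3% |
| 80 | 30 | 6.7% | 15.4% | 27.5% | 44.8% |
| 80 | 50 | 18.9% | 26.2% | 36.4% | 46.4% |
| 40 | 30 | 14.6% | 23.1% | 33.4% | 45.3% |

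Hand check at N = 80, SD 30: the standard error is 30/√80 = 3.35. With no one off drug, Φ(−5/3.35) = 6.8%. With 20% off drug the mean is −12, and Φ(−2/3.35) = 27.5%.

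**Step 3: men who withdraw.** The same setting (N = 80, SD 30, fall of 15%, 20% of men off drug) depends on an unwritten rule:

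- Off-drug values measured: mean −12.0, wrong verdict 27.5%.
- Baseline value carried forward: mean −12.0, wrong verdict 25.9%.
- Dropped at random: mean −15.0, wrong verdict 9.0%. There is no dilution; the rise from 6.7% comes from having 64 men instead of 80. This is also no longer an intention-to-treat analysis.

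**Step 4: larger falls.** With a true fall of 20%, N = 80, SD 20–30 and up to 20% off drug, the chance of a wrong verdict is at most about 4%. The exposure is mainly to moderate falls just beyond the margin.

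**The case against.** The case against has real weight.

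- **Only is inferred from silence.** Section 5.3 promises an intention-to-treat analysis and does not forbid others. That is so, but section 10 adds none, and a set chosen after the data are seen carries little weight.
- **The off-drug shares are invented.** No section supports 20% or 30%, and section 1.2 cites an earlier study of this product with few discontinuations. This stands as a limit on size. Discontinuation is not the same as skipped doses, however, so it does not settle the matter.
- **The shift is small beside the noise.** At the margin it is about 2.5 points with 20% off drug, against an assumed standard error of 3.35. True, but the shift runs in one direction and favours the claim.
- **Testosterone offers a partial check.** Section 1.3 also expects testosterone to rise significantly, and widespread non-use would weaken that result. A mean rise could still appear with a fifth of the men off drug.

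A reader might infer several stronger things that the documents do not support:

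- That men who withdraw necessarily dilute the result. Step 3 shows that this turns on a missing-data rule the plan does not give.
- That the listed withdrawal reason shows compliance is already being assessed. It is a single example in a list, with no measure behind it.
- That LH and FSH share the flaw in the same form. Section 1.3 expects no significant impact on them, but the ±10% rule covers sperm count only.
- That an on-drug analysis should replace intention to treat. If men with large falls leave, the on-drug set also favours no change.

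**Conclusion.** The point holds in a limited form. The plan aims to show no change in sperm count and names one analysis population, the one in which unrecorded non-use favours that aim. The direction is clear for men who skip the drug, remain in the study, are sampled and stay near baseline, provided the drug has a real effect. The size cannot be known from the documents. On assumed off-drug shares of 20% and 30% with no change off drug, on-drug falls of about 12.3–12.5% and 14.0–14.3% read as −10%.

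The rank of sperm count is itself unsettled: secondary in section 3.2, within the primary endpoint in section 10.1, and with semen parameters exploratory in section 10.2. It is nevertheless the only quantity in the formal hypothesis. Whether the ±10% criterion should be applied to a confidence interval is a separate issue. An interval rule would not remove this problem: at N = 80, SD 30 and a true on-drug fall of exactly 10%, requiring the 90% interval to lie inside ±10% gives a false-claim rate of 5.2% with everyone on drug and 14.2% with 20% off drug and measured.

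This is an inexpensive safeguard worth adding; it does not show that the trial's result would be wrong.

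**What to change.** 1. Keep the intention-to-treat analysis. Define who is in it, and state how the semen values of withdrawn men enter it.
2. Pre-specify an on-drug analysis of sperm count. Fix the adherence definition before data review, using product returned at Visits 4 and 6. Do not define adherence by testosterone, which is itself a primary outcome; doing so would select men on an outcome.
3. Conclude no change only if both analyses meet the plan's ±10% criterion, and report any disagreement between them.

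**Cost.** One paragraph in the statistical section and a count of returned product at two visits already scheduled; no extra visits or assays.

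**Downsides.** The claim becomes harder to meet and the on-drug set is smaller. With a true change of zero, SD 30 and the mean-change rule, the chance of meeting the criterion is 2Φ(10/3.35) − 1 = 99.7% in 80 men and 2Φ(10/3.75) − 1 = 99.2% in an on-drug set of 64, so at least 98.9% for both. Starting from 40 men, it is 96.5%, and 94.1% in an on-drug set of 32, so at least 90.6% for both. The on-drug set is also open to selection, so it supplements the intention-to-treat analysis and does not replace it.

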6. PATIENT SELECTION/ELIGIBILITY CRITERIA

6.1 Inclusion (Eligibility) Criteria

Subjects must meet the following criteria:

1. Voluntarily sign and date the study consent form(s) which have been approved by an Institutional Review Board (IRB). Written consent must be obtained prior to the initiation of any study procedures.
2. Male between 18 and 55 years of age, inclusive, with documented onset of hypogonadism prior to age 55.
3. Documented diagnosis of primary hypogonadism (congenital or acquired) or hypogonadotropic hypogonadism (congenital or acquired).
4. Serum total testosterone < 350 ng/dL based on 2 consecutive blood samples obtained 1-4 weeks apart between 6 and 10 AM following an appropriate washout of current androgen replacement therapy; with clinical symptoms of hypogonadism such as diminished energy and sexual function; and/or a decreased sperm count (<20 million sperm/mL semen).
5. Naïve to androgen replacement or has discontinued current treatment and completed a washout of 4 weeks following androgen treatment (excluding Testopel TM). Washout must be completed prior to collection of baseline serum testosterone samples to determine study eligibility.
6. Judged to be in good general health as determined by the principal investigator based upon the results of a medical history, physical examination, vital signs, and laboratory profile and a 12-lead electrocardiogram (ECG) performed at the time of enrolment of within the previous 6 months.

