1.3 Study Rationale

Current advantages to Natesto TM include ease of delivery and decreased risk of the medication being transfer upon skin contact to woman or children.¹¹ Recently Natesto 4.5% NTG (125 uL/nostril, 11.0mg testosterone/dose) TID dosing was shown to also increase serum testosterone while maintaining normal, though decreased, serum levels of LH and FSH.¹⁶ This has the

theoretical benefit of maintaining normal semen parameters while on TRT with Natesto- to date, this theoretical benefit has not been evaluated.

While Natesto has been shown to have positive effects on Testosterone while maintaining LH and FSH, the impact on sperm count has not yet been proven. Past research has shown a marked reduction in spermatogenesis in topical testosterone gel treatment.¹⁷ Natesto™ has the potential to maintain normal spermatogenesis levels via maintenance of FSH and LH levels in the normal range. Our hypothesis is that Natesto™ will significantly increase Testosterone while having no significant impact on FSH, LH, and serum parameters in men with Low testosterone. A proposed mechanism for this is that the TID dosing of Natesto will maintain pulsatile release of GnRH, preventing marked decreases in serum FSH and LH.

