6.2 Exclusion (Eligibility) Criteria

Subjects meeting any of the following criteria will be excluded from the study:

1. History of significant sensitivity or allergy to androgens, castor oil or product excipients.
2. Clinically significant findings in the pre-study examinations including abnormal breast examination requiring follow-up.

3. Abnormal prostate digital rectal examination (DRE) with palpable nodule(s) or I-PSS score > 19 points.
4. Body mass index (BMI) ≥ 35 kg/m².
5. Azoospermia or severe oligospermia (<1 million sperm/cc) on screening semen analysis: no sperm found in direct nor centrifuged semen sample or previous history of vasectomy.
6. Clinically significant abnormal laboratory value, in the opinion of the investigator, in serum chemistry, hematology, or urinalysis including but not limited to:
 - a. Baseline hemoglobin > 16 g/dL
 - b. Hematocrit < 35% or > 50%
 - c. PSA > 4 ng/mL and age >40
7. History of seizures or convulsions, including febrile, alcohol or drug withdrawal seizures.
8. History of any clinically significant illness, infection, or surgical procedure within 4 weeks prior to study drug administration.
9. History of stroke or myocardial infarction within the past 5 years.
10. History of, or current or suspected, prostate or breast cancer.
11. History of diagnosed, severe, untreated, obstructive sleep apnea.
12. History of abuse of alcohol or any drug substance in the opinion of the investigator within the previous 2 years.
13. History of nasal disorders such as nasal polyps; nasal septal perforation; nasal surgery; nasal trauma resulting in nasal fracture within the previous 6 months or nasal fracture that caused a deviated anterior nasal septum; sinus surgery or sinus disease
14. Donation or loss of 550 mL or more blood volume (including plasmapheresis) or receipt of a transfusion of any blood product within 12 weeks prior to the start of treatment.
15. Inadequate venous access for collection of serial blood samples required for pharmacokinetic profiles.
16. Receipt of any investigational product within 4 weeks or within 5 half-lives prior to the start of treatment.

17. Inability to understand and provide written informed consent for the study.
18. Considered by the investigator or the sponsor-designated physician, for any reason, that the subject is an unsuitable candidate to receive Natesto.
19. History of treatment with clomiphene citrate within the last 12 months.
20. History of varicocele repair.

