7.3 Pre-Treatment Procedures and Evaluations

Upon evaluating the inclusion/exclusion criteria, patients will be recruited to the study. Patients will be instructed to stop any use of androgen replacement for 4 weeks prior to first treatment session and refrain from using any other androgen replacement therapy option during the study. After the washout period and before the first treatment session, patients will answer the IIEF-EF and SF-36 questionnaires for baseline evaluation.

7.4 Follow-Up Procedures and Evaluations:

Follow-up visits will be conducted at week 14+/- 7 days and 26+/- 7 days, these visits shall include:

- Measuring IIEF-EF and SF-36 scores of patients at the clinic
- Taking serum FSH, LH, E, and total Testosterone levels
- Semen analysis
- Reporting and recording adverse events at every follow-up visit.

Additional determinations of total serum testosterone will be performed periodically at every follow up visit, beginning one month after initiation of therapy. Additional semen analysis will be performed at weeks 15+/- 7 days and 27+/- 7 days.

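### Androgen-naïve men and men 4 weeks off androgens enter one cohort, and 10.4 neither stratifies nor adjusts for prior use, so recovery from earlier suppression could dilute or hide a fall in sperm count.

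*Combined protocol and SAP*

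**What the plan says.** Section 6.1, item 5, opens two routes into the study: "Naïve to androgen replacement or has discontinued current treatment", the latter with the man having "completed a washout of 4 weeks following androgen treatment (excluding Testopel TM"). No cap or quota is set on either route. The washout is tied to testosterone alone: "Washout must be completed prior to collection of baseline serum testosterone samples to determine study eligibility". Section 7.3 describes it differently, after recruitment and relative to first dosing: "Patients will be instructed to stop any use of androgen replacement for 4 weeks prior to first treatment session". Neither place asks for LH, FSH or sperm count to be stable.

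Item 4 lists, as part of the indication, "and/or a decreased sperm count (<20 million sperm/mL semen"). Exclusion 5 in section 6.2 removes azoospermia and counts below 1 million/cc. Section 1.3 states: "Past research has shown a marked reduction in spermatogenesis in topical testosterone gel treatment".

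Sections 3.1, 3.2 and 10.1 define the outcomes as changes from baseline. Sections 2.1 and 10.4 make the sperm-count claim one of change within ±10%. On method, section 10.4 says: "Change in sperm count will be analyzed using the ANOVA and MANOVA". LH and FSH get a one-sample t-test. Prior androgen use appears nowhere in 10.4.

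**The concern.** With no comparator, each man's baseline stands in for what his count would have been without Natesto. That works if the baseline is stable. For a man recently off another testosterone product it may not be: the protocol itself reports suppression under topical gel, and nothing shows that the effect has gone by the time of his baseline sample. If he is still recovering, his count drifts up while any Natesto effect pushes it down.

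The direction matters. The study hopes to conclude no change, so upward drift in some men favours its own hypothesis when the drug is harmful. If the drug is neutral, the same drift reads as a rise. A larger sample does not help; it narrows the interval around a shifted value. The same could happen to LH and FSH if they too are still suppressed at baseline.

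**Working it through.** The plan has no figure to reproduce: it gives no SD, expected effect or power, and no share of previously treated men. What follows is an illustration.

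**Inputs**
- From the documents: the ±10% margin (2.1, 10.4); N of 80 (6.3, 10.3) or 40 (4.1).
- Assumed: true Natesto-related fall *d*; residual suppression *s* at baseline, relative to a man's own unsuppressed level; full recovery by week 26; share previously treated *p*.

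**Formula.** A naïve man's count is multiplied by (1 - d). A previously treated man's is multiplied by (1 - d)/(1 - s). The combined log change is

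ln(1 - d) - p·ln(1 - s).

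**Worked case, d = 20%, s = 50%, p = 20%:** -0.223 + 0.2 × 0.693 = -0.085, which is -8.1%.

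| d | s | p | Combined change |
|---|---|---|---|
| 20% | 50% | 10% | -14.3% |
| 20% | 50% | 20% | -8.1% |
| 20% | 50% | 30% | -1.5% |
| 20% | 25% | 10% | -17.7% |
| 20% | 25% | 40% | -10.2% |
| 0% | 50% | 30% | +23.1% |

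**Share at which the fall enters ±10%.** Set the combined log change to ln(0.9) = -0.105:
- d = 20%, s = 50%: (0.223 - 0.105)/0.693 = 17%.
- d = 20%, s = 25%: (0.223 - 0.105)/0.288 = 41%.
- d = 30%, s = 50%: (0.357 - 0.105)/0.693 = 36%.
- d = 50%, s = 50%: (0.693 - 0.105)/0.693 = 85%.

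**Other summaries.** The plan does not say which summary the ±10% applies to. For d = 20%, s = 50%:
- Ratio of mean counts, (1 - d)/(1 - ps) - 1: the threshold is (1 - 0.8/0.9)/0.5 = 22%.
- Mean of individual percentage changes, -d + p(1 - d)s/(1 - s): the threshold is 0.10/0.80 = 12.5%.

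At s = 25% these become 44% and 37.5%. The direction is the same and the threshold moves.

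**Chance of a wrong no-change result.** Apply ±10% to the point estimate, with N = 80, d = 20%, s = 50% and a normal approximation on the log scale. With assumed within-group log-SD σ, the variance is σ² + p(1 - p)(ln 0.5)². For σ = 0.4 and p = 25%, the mean is -0.223 + 0.173 = -0.050 and the SE is √((0.160 + 0.090)/80) = 0.056. The chance of landing inside ±10% is then 84%, against 0.4% at p = 0. For σ = 0.6 the figures are 74% and 4%.

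**Naïve men alone.** At p = 25% there are 80 × 0.75 = 60. The SE is 0.4/√60 = 0.052, and the distance from the margin is (0.223 - 0.105)/0.052 = 2.28 SE, so the chance is about 1.1%. At σ = 0.6 it is about 6.4% (1.52 SE).

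No figures are given for LH and FSH, because the documents offer no basis for *s* in either.

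**The case against.** The strongest reply is that the driving premise is not in the documents. Section 1.3 describes suppression during gel treatment. It is silent on sperm count 4 weeks after stopping, on the speed of recovery, and on LH or FSH after earlier therapy. That stands, so residual suppression has to remain an assumption. A reader might also infer that these men's own testosterone would recover; item 3 requires documented primary or hypogonadotropic hypogonadism, so this cannot be presumed.

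Exclusion 5 is a real but partial safeguard. It removes the most suppressed men, leaves counts of 1 million/mL and above, and does nothing for LH or FSH.

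Three stronger readings are tempting, and the documents do not carry them:
- That the entry criteria select unrecovered men. A low count is one branch of an and/or, testosterone below 350 ng/dL is equally what untreated hypogonadism looks like, and under items 4 and 5 the second testosterone sample falls at least 4 + 1 = 5 weeks after stopping.
- That the plan concedes slow recovery. Section 6.2 does exclude "History of treatment with clomiphene citrate within the last 12 months", but gives no reason for that window, and no reason is given for the week-14 semen sample.
- That 10.4 states the two kinds of men are combined. This is inferred from silence. Its groups A and B are undefined, so they are not a safeguard either.

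Finally, 7.2 already calls for medication history and 11.5 for source records sufficient to verify entry criteria. A split by prior use could therefore be made afterwards, but none is planned.

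**Conclusion.** The concern holds as a gap in design and analysis. Two kinds of men enter, stability of the outcomes is not required, no comparator is described, and nothing in 10.4 separates recovery from drug effect. If residual suppression exists, the bias runs toward the study's own hypothesis.

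Its size is unknown. Hiding a 20% fall takes about a 17% share at 50% residual suppression and about 41% at 25%; hiding a 30% fall at 50% suppression takes about 36%. With few previously treated men and mild suppression (10% share, 25%), the fall is diluted to -17.7% and stays visible. All of this rests on assumed suppression, full recovery and share. For LH and FSH the same mechanism is possible but has no figures behind it.

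A reader might conclude that a harmful effect would be masked, or that washed-out men must be kept out of the analysis. The documents support neither. The first depends on quantities they do not give. The second conflicts with the intention-to-treat statement in 5.3 and would cut a sample whose size is itself unsettled (40 or 80). Confidence in the gap is high, and in its practical size moderate at best.

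**What to change.** - Add two CRF fields: last androgen product and date of last use.
- Prespecify in 10.4 that change in sperm count, LH and FSH is estimated and reported by prior-use stratum (naïve, washout), with prior use as a factor in the model.
- State that the ±10% conclusion is claimed only if it also holds in the naïve men. Continue to report all enrolled men.
- Reconcile the Testopel parenthesis in item 5, which can mean that pellet users are barred or that the 4-week rule does not apply to them. Reconcile the timing of washout between 6.1 and 7.3. No washout length is proposed here.

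The cost is a wording change, two fields and one stratified analysis. The price in precision is a wider interval in the naïve stratum: with an assumed 25% washout share and the same SD, 60 of 80 men remain and the naïve-only interval is √(80/60) = 1.15 times as wide as one from 80 such men. If few men enter through washout, little is lost; if many do, the combined estimate is the one most exposed.
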